1. STATISTICAL METHODS

1.1 Sample Size Determination

The main indicator of this study was the incidence of adverse events in the treatment of Alzheimer's disease with 10 mg donepezil hydrochloride tablets. According to the safety data in the comprehensive literature, the incidence of adverse events is basically between 69.4%-81%, and the expected total incidence of adverse events is about 76%, estimated with a 95% confidence interval. With reference to the research data, the width of the confidence interval for the incidence of adverse events is 8%, and the significance

level is set as 0.05. The sample size is estimated to be 461 cases by using PASS11.0 software. Considering the 20% drop out rate, 554 cases are finally enter the group.

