**Safety and Efficacy of Donepezil in Mild to
Moderate Alzheimer's Disease: A Multi-center
Single-arm Study in China**

Protocol & SAP Synopsis

2016.10.09

NCT02787746

PROTOCOL TITLE	Safety and Efficacy of Donepezil in Mild to Moderate Alzheimer's Disease: A Multi-center Single-arm Study in China
STUDY SPONSOR	Beijing Friendship Hospital & Eisai (China) Pharmaceutical Co., Ltd.
STUDY PHASE	4
INDICATION	For the treatment of mild to moderate Alzheimer's disease.
PRIMARY ENDPOINT	Monitoring and recording the count and incidence of adverse events (AEs).
SECONDARY ENDPOINTS	
 • Monitor and record the number of patients withdrew from trial for adverse events. • Change from baseline to 20 weeks in MMSE scores. • Change from baseline to 20 weeks in ADL scores. • Correlation analysis between Apo-E genotyping and adverse events of donepezil.
STUDY DESIGN	This is a Phase 4 multi-center, single-arm, open labeling study.
SAMPLE SIZE	The main indicator of this study was the incidence of adverse events in the treatment of Alzheimer's disease with 10 mg donepezil hydrochloride tablets. According to the safety data in the comprehensive literature, the incidence of adverse events is basically between 69.4%-81%, and the expected total incidence of adverse events is about 76%, estimated with a 95% confidence interval. With reference to the research data, the width of the confidence interval for the incidence of adverse events is 8%, and the significance level is set as 0.05. The sample size is estimated to be 461 cases by using PASS11.0 software. Considering the 20% drop out rate, 554 cases are finally planned to enter the group.

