1.3 Analysis Populations

Full Analysis Set (FAS) refers to the ideal subject set as close as possible to the principle of intention analysis (the main analysis includes all randomized subjects). The data set is obtained by excluding all randomized subjects with the smallest and reasonable method. For the estimation of the missing values of the main variables, the last carry-forward obsevation (LOCF) was used to the point where the test data was missing, and the number of subjects who evaluated the efficacy at the end point of each group was consistent with that at the beginning of the test .

Per-Protocol Set (PPS) is composed of all cases that meet the test protocol, have good compliance (the actual dose takes 80% to 120% of the applied dose), do not take prohibited drugs during the test, and complete the contents specified in CRF.

Safety Analysis Set (SAS) is composed of all cases taking drugs at least once and having safety evaluation at least once.

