Safety and Efficacy of Donepezil in Mild to Moderate Alzheimer's Disease: A Multi-center

Single-arm Study in China

NCT02787746

September 18, 2016

Statistical Analysis Plan (SAP)

Safety analysis is conducted on the safety set (SS, patients who receive at least one dose of donepezil 10mg/day and have at least one safety evaluation). Efficacy analysis is conducted on the per protocol analysis set (PPS, patients who complete the study with no major protocol violations) with last observation carried forward (LOCF) as well as the full analysis set (FAS, all enrolled patients are included) LOCF. In addition, in order to test the robustness and accuracy of our results, efficacy analysis is further conducted on the PPS and FAS wherein missing data is not filled in and not included and thus only actual data of every patient who take the efficacy test are included (FAS [actual number] and PPS [actual number], respectively).

For the safety analysis, overall incidence of AEs and SAEs, incidence of AEs and SAEs by organ systems, severity, and AEs' relationship to donepezil are calculated and/or assessed by calculating the number of patients having AEs and SAEs, the prevalence of AEs and SAEs and their 95% confidence intervals (95% CI). Laboratory abnormalities such as changes in alanine aminotransferase (ALT) and aspartate aminotransferase (AST), and changes in EKG and ECG such as HR, QT, QTc are summarized and described using means, standard deviation (SD), median, maximal, minimal, 25th and 75th percentile values, and further analyzed with paired *t*-test. Correlations of AEs and various risk factors are first assessed with univariate logistic regression analysis, and variables included patients' medical history (history of neurological, cardiovascular, mental, liver and gastrointestinal diseases), age (grouped into ≤ 75 and > 75 years), gender, body weight (≤ 55 kg and > 55 kg), APOE genotype ($\epsilon 2/\epsilon 2$, $\epsilon 3/\epsilon 3$, $\epsilon 4/\epsilon 4$, $\epsilon 2/\epsilon 3$, $\epsilon 2/\epsilon 4$, and $\epsilon 3/\epsilon 4$), the presence or absence of APOE $\epsilon 4/\epsilon 4$, concomitant medications (cardiovascular and cerebrovascular, gastrointestinal, liver, neurological, mental and hypoglycemic medications), and duration of donepezil 5mg/day treatment prior to the study (days). Forward stepwise multivariate logistic regression analysis is subsequently performed to

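### The 20% dropout allowance was multiplied onto 461 instead of divided out: 554 enrolled covers a 16.8% loss, not 20%, with little effect on the precision of the AE incidence

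*Protocol*

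**What the plan says.** Section 1.1 of the protocol sizes the study on the precision of the AE incidence at 10 mg. It takes an overall incidence of about 76%, from a literature range of 69.4% to 81%, and asks for a 95% confidence interval with a total width of 8%. From this, "The sample size is estimated to be 461 cases by using PASS11.0 software". The next sentence makes the dropout allowance: "Considering the 20% drop out rate, 554 cases are finally enter the group". The sample size row of the synopsis repeats the derivation and ends "Considering the 20% drop out rate, 554 cases are finally planned to enter the group". Neither place writes out the formula that leads from 461 to 554.

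The denominator for AE incidence is set elsewhere. The SAP runs the safety analysis on the safety set, defined as "patients who receive at least one dose of donepezil 10mg/day and have at least one safety evaluation". Protocol section 1.3 is similar: "Safety Analysis Set (SAS) is composed of all cases taking drugs at least once and having safety evaluation at least once". Neither definition requires completion of the 20 weeks.

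**The concern.** The three figures 461, 20% and 554 do not fit together if the dropout rate has its ordinary meaning, a fraction of the patients who enter. Removing 20% of 554 does not leave 461. The total agrees instead with adding 20% of 461 to 461, which is a smaller allowance than the one stated.

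This paragraph is the only quantitative justification for the enrolment target. At stake is whether the trial would still deliver the 8-point interval at its own assumed loss, and whether a reader can rely on the stated allowance.

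**Working it through.** **Inputs** (protocol section 1.1 and synopsis): expected incidence p = 0.76; two-sided 95% interval; total width 0.08; 461 before dropout; dropout 20%; 554 enrolled. The documents name no interval method, either for planning or for analysis (protocol section 1.7 and the SAP ask only for confidence intervals).

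**Step 1: reproduce 461.** The smallest n whose 95% interval at p = 0.76 is no wider than 0.08:

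| Method | Smallest n |
|---|---|
| Exact (Clopper-Pearson) | 461 |
| Wilson with continuity correction | 461 |
| Wald with continuity correction | 463 |
| Wald | 438 |
| Wilson | 436 |

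The exact width is B(0.975; x+1, n−x) − B(0.025; x, n−x+1), where x = np and B is the beta quantile. It is 7.996 points at n = 461 and 8.005 at n = 460. The 461 is therefore sound, and I use the exact interval below because it reproduces that figure.

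**Step 2: reproduce 554.**

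- Multiplier: 461 × (1 + 0.20) = 553.2, rounded up to 554. This is the stated total.
- Divisor: 461/(1 − 0.20) = 576.25, rounded up to 577. This is not the stated total; it is 577 − 554 = 23 patients more (23/554 = 4.2%).

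**Step 3: what 554 covers.**

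- After a 20% loss: 554 × 0.80 = 443.2, so about 443 remain.
- Largest loss that still leaves 461: 554 − 461 = 93, and 93/554 = 16.8%.

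**Step 4: effect on the AE interval.** What counts is the number in the safety set. The documents do not give the fraction expected to be excluded from it, so this is a range (exact width at 76%, n rounded down):

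| Excluded from safety set | n | Width (points) |
|---|---|---|
| None | 554 | 7.28 |
| 5% | 526 | 7.48 |
| 10% | 498 | 7.69 |
| 16.8% (93 patients) | 461 | 8.00 |
| 20% | 443 | 8.16 |

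At the bottom of the range the excess over target is 8.16 − 8.00 = 0.16 points, or 0.08 per side. At n = 443 the Wald width is 7.95 and the Wilson width 7.93, both within 8.

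**Step 5: compare with the uncertainty in the incidence.** At n = 461 the exact width is 8.61 points if the incidence is 69.4% and 7.37 if it is 81%. The protocol's own literature range moves the width by 8.61 − 7.37 = 1.24 points, far more than the dropout step does.

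**The case against.** No formula is written down, so the multiplication is inferred. The text does not say that the 20% is a share of those enrolled, or that 461 must remain; if the sponsor meant an allowance of 20% added to 461, then 554 is right. The precision consequence is also slight. Dropouts with a dose and a safety evaluation stay in the AE denominator, so 8.16 points arises only if the full 20% leave the safety set, and nothing in the documents predicts that. Nor is 8 a sharp line: the exact width at n = 443 is 7.99 if the incidence is 77.5%, and at n = 461 with a whole number of events (350, since 0.76 × 461 = 350.36) it is already 8.005. Finally, the SAP already names the analysis set for AEs, so the sample-size paragraph need not repeat it.

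Most of this stands as a limit on the consequence, and it is why the point is minor. It does not rescue the sentence. The inference is tight, because the multiplier gives exactly 554 and the divisor does not. A dropout rate attached to patients entering a study is ordinarily a share of those patients; a different base would have to be stated. On the ordinary reading the allowance falls short of what is claimed. Naming the safety set in the sample-size text is a useful clarification and not the correction of an error.

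**Conclusion.** The concern holds, as a minor arithmetic error. The 461 is correct for an exact 95% interval; the step to 554 is not the inflation for a 20% loss. The enrolment target covers a loss of 93 patients (16.8%), where 577 would be needed to cover 20%.

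The 8-point width has not been shown to be missed. With exact intervals at 76%, the expected width lies between 7.28 and 8.16 points as exclusions from the safety set go from none to 20%. The primary analysis is not threatened. What is wrong is the stated justification.

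This rests on two assumptions: that the 20% refers to patients enrolled, and that the interval is exact. The first is the ordinary meaning of a dropout rate. The second is inferred from the agreement with 461.

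**What to change.** Replace the dropout sentence in the synopsis (sample size row) and in protocol section 1.1 with wording such as:

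> Enrolling 554 patients retains 461 in the safety set if no more than 93 (16.8% of those enrolled) are excluded from it. At an incidence of 76%, the expected width of the exact (Clopper-Pearson) 95% confidence interval is 7.3% if none are excluded (n = 554) and 8.2% if 20% are excluded (n = 443).

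This states the loss actually covered, ties precision to the analysis set that determines it, and names the interval method behind the widths. The cost is one sentence in each of two places, with no extra patients, visits or analyses. Raising enrolment to 577 is not needed.

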1.2 Elimination criteria

1. After the clinical study started, it was found that the subjects did not meet the case inclusion criteria or the case exclusion criteria.
2. Subjects had poor compliance and never used study medication.
3. Those who seriously violate the research plan.

1.3 Analysis Populations

Full Analysis Set (FAS) refers to the ideal subject set as close as possible to the principle of intention analysis (the main analysis includes all randomized subjects). The data set is obtained by excluding all randomized subjects with the smallest and reasonable method. For the estimation of the missing values of the main variables, the last carry-forward obsevation (LOCF) was used to the point where the test data was missing, and the number of subjects who evaluated the efficacy at the end point of each group was consistent with that at the beginning of the test .

Per-Protocol Set (PPS) is composed of all cases that meet the test protocol, have good compliance (the actual dose takes 80% to 120% of the applied dose), do not take prohibited drugs during the test, and complete the contents specified in CRF.

Safety Analysis Set (SAS) is composed of all cases taking drugs at least once and having safety evaluation at least once.

1.4 Efficacy Endpoints

- Primary Efficacy Endpoints

Monitoring and recording the count and incidence of adverse events (AEs).

- Secondary Efficacy Endpoints

1. Monitor and record the number of patients withdrew from trial for adverse events.
2. Change from baseline to 20 weeks in MMSE scores.
3. Change from baseline to 20 weeks in ADL scores.
4. Correlation analysis between Apo-E genotyping and adverse events of donepezil.

1.5 Safety Endpoints

Laboratory indicators, vital signs, weight and ECG

The laboratory inspection indicators include:

1. Blood routine: red blood cell count RBC, hemoglobin HGB, platelet count PLT, white blood cell count WBC.
2. Urine routine: urine protein PRO, urine red blood cell count URBC, urine white blood cell count UWBC, urine ketone body KET.
3. Blood biochemistry: liver function (ALT, aspartate aminotransferase AST, alkaline phosphatase ALP, total bilirubin TBIL, γ -glutamyl transferase γ -GT, total protein TP), renal function (creatinine Cr, Urea nitrogen BUN), myocardial enzymes (creatine kinase CK, lactate dehydrogenase LDH), fasting blood glucose GLU, electrolytes (Na^+ , K^+ , Cl^- , Ca^{2+}).

1.6 Statistical Methods

Complete details of efficacy and safety analyses will be provided in a separate Statistical Analysis Plan (SAP).

1.7 Efficacy Analysis

1. Primary indicators analysis

For the incidence of adverse events, list the number of subjects with adverse events, and calculate the incidence and confidence interval, and at the same time list the number of various adverse events and their incidence and confidence interval.

2. Secondary indicators analysis

The analysis of the loss rate caused by adverse events is the same as the adverse events.

For the changes in MMSE and ADL scores, list the mean, median, standard deviation, maximum, minimum, 25%, and 75% quantiles. The paired t-test should be carried out for the scores before and after treatment to obtain 95% confidence interval of the changes before and after treatment.

1.8 Other Safety Data Analysis

For the QT interval and heart rate before and after treatment, the mean, median, standard deviation, maximum, minimum, 25%, 75% quantiles were used for statistical description, and the scores before and after treatment were paired t-tested. At the same time, the 95% confidence interval of the change value before and after treatment is obtained. Based on the predetermined MCID value, the 95% confidence interval is compared with the lower limit of the 95% confidence interval to determine whether the changes in QT interval and heart rate have clinical significance.

For vital signs, the mean, median, standard deviation, maximum, minimum, and 95% confidence intervals were used to describe the changes in vital signs at each follow-up point.

For laboratory examination and ECG, the clinical significance judgment and frequency (or frequency) of all indexes before and after treatment are made in a cross table, and the details of abnormal examination items after treatment are listed.

For quantitative laboratory test values, list the mean, median, standard deviation, maximum, minimum, 25%, 75% quantiles, and paired t-test for the scores before and after treatment to obtain 95% confidence interval of the changed value to evaluate its safety.

● **Adverse Events**

When filling out the adverse event form, the researcher should use mild, moderate, and severe to describe the intensity of the adverse event. To unify the standard, the classification of event intensity is as follows:

Moderate: To some extent affects the normal function of the subject.

Severe: Obviously affect the normal function of the subject.

- Mild: Does not affect the normal function of the subject.
- Moderate: To some extent affects the normal function of the subject.
- Severe: Obviously affect the normal function of the subject.

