ELIGIBILITY CRITERIA	
Inclusion Criteria:
 
 1. Patients between 50 and 85 years of age. 2. Patients newly diagnosed as probable AD based on Diagnostic and Statistical Manual of Mental Disorders, 4th Edition, Text Revision (DSM-IV-TR) criteria and National Institute of Neurologic and Communicative Disorders and Stroke—AD and Related Disorders Association (NINCDS-ADRDA) criteria; Mild to moderate AD with Mini-Mental State Examination (MMSE) 10-24, modified Hachinski ischaemic scale (MHIS)≤4, Activity of daily life scale (ADL)≥23, and Hamilton Depression Scale (HAMD) <7. 3. MRI image supports the diagnosis of AD (medial temporal lobe atrophy, Fazekas scale of white matter lesions≤2 within 6 months prior to the screening). 4. 5mg daily of Donepezil for at least four weeks before the screening. 5. Patient with exclusive caregiver. 6. Patient should be ambulatory or ambulatory aided by a walker or cane. 7. With good eyesight and hearing, can cooperate with the examination and treatment. 
Exclusion Criteria:
 
 1. Patients with vascular dementia, other types of dementia or with other psychiatric or neurological disorders (e.g. delirium, depression, Parkinson's disease, etc.). 2. Patients with type I diabetes, obstructive lung disease or asthma, vitamin B₁₂ or folic acid deficiency, thyroid dysfunction, severe liver or kidney dysfunction, severe cardiac insufficiency (congestive heart failure, myocardial infarction, sick sinus syndrome, II-III degree atrioventricular block or heart rate<50 beats/minute [bpm]). 3. Epilepsy or head trauma resulting in unconsciousness that occurred in the two years prior to the screening. 4. Patients with hematologic diseases (such as anemia, granulocytes, leukemia, etc.), tumor, neoplasms within 2 years prior to the screening. 5. Patients with a history of alcohol dependence and drug abuse. 6. Patients with known hypersensitivity to medicines or
----------------------	---

	
foods;
 
 7. Patients taking anticholinergic agents or antihistaminic agents; 8. Patients who had been hospitalized continuously for more than 3 months before the screening.

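### Minor: the protocol's rule for judging QT and heart-rate change compares the 95% CI with its own lower limit, and the SAP does not correct it

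*Protocol*

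**What the plan says.** Protocol section 1.8 (Other Safety Data Analysis) first describes QT interval and heart rate before and after treatment and applies a paired t-test. It then says that "the 95% confidence interval of the change value before and after treatment is obtained". That is the only interval formed for these two variables.

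The next sentence is the decision rule. It opens "Based on the predetermined MCID value" and continues that "the 95% confidence interval is compared with the lower limit of the 95% confidence interval to determine whether the changes in QT interval", or those in heart rate, are clinically significant. It gives no sign for the MCID, no order of subtraction and no statement of what follows if the criterion is not met.

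Protocol section 1.6 leaves full detail of the safety analyses to a separate SAP. In the SAP, "changes in EKG and ECG such as HR, QT, QTc are summarized and described" with the usual summary measures "and further analyzed with paired *t*-test". The SAP attaches 95% confidence intervals to adverse-event and serious-adverse-event rates. For heart rate, QT and QTc it mentions no confidence interval, no MCID and no criterion for clinical significance.

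**The concern.** A rule for clinical relevance has to set the estimate, with its uncertainty, against an external threshold. Here the two things compared are an interval and one end of that same interval. The threshold is mentioned in the opening words but takes no part in the comparison.

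This is the only rule in either document for deciding whether a mean change in QT or heart rate matters clinically. The ECG cross-table in section 1.8 tabulates clinical-significance judgments before and after treatment; it does not set a mean change against an MCID. If the sentence stays as it is, whoever analyses the data must choose the limit, the sign and the conclusion, possibly after seeing the results.

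**Working it through.** The documents give no figure for this rule, so there is none to reproduce. The check is of logic, followed by an illustration.

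**Inputs.** From protocol 1.8: a 95% CI of the paired change, and an MCID described as predetermined. From the SAP: two-sided analysis. From protocol 1.1: n = 461, used only to give the illustration a scale. Assumed, because the documents give neither: SD of the change 15 to 30 units, and MCID M = 10 units. These are arbitrary test values, not proposed thresholds.

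**Step 1: the rule as written.** Call the interval [L, U]. Comparing it with L asks where [L, U] lies relative to L. Since U ≥ L always, the interval always starts at L and extends upward from it. M does not enter.

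Illustration with SD 20: half-width = 1.96 × 20 / √461 = 1.83.

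| Mean change | 95% CI | Position relative to its own lower limit |
|---|---|---|
| 0 | -1.83 to 1.83 | starts at it, lies above it |
| +20 | 18.17 to 21.83 | starts at it, lies above it |

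No change and a large change get the same answer.

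**Step 2: does the SAP repair it?** Protocol 1.6 points to the SAP, and the SAP has no such rule. The SAP is dated 18 September 2016 and the protocol synopsis 9 October 2016, so the dates do not show that the SAP replaced the protocol sentence.

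**Step 3: the likely intended rule, L against M.** Take change as after minus before.

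- L > +M shows a relevant increase. This part works.
- L > +M can never be met by a decrease. With a mean change of -15 and SD 20, the CI is -16.83 to -13.17. L is far below +10, so nothing is flagged, although the whole interval lies below -10.
- Switching to L < -M does not help. With a mean change of -9 the CI is -10.83 to -7.17. L is below -10, but most of the interval, including the estimate, is not. Showing a decrease needs U < -M.

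In probabilities (normal approximation, n = 461, SD 15 to 30, true mean change a decrease of M + 5 units):

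- P(L > +M) = 0.000 at every SD tried.
- P(U < -M) = Φ(5/SE - 1.96), with SE = SD/√461.
- SD 15: SE = 0.699, and the probability is 1.000.
- SD 30: SE = 1.397, so Φ(3.58 - 1.96) = 0.947.

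M cancels, so these results are the same for M = 5 and M = 10.

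**Step 4: what a two-limit rule does.** Conclude an increase if L > +M, a decrease if U < -M, absence only if -M < L and U < +M, and otherwise inconclusive. If the true mean change is exactly +M, then P(L > +M) = 2.5% and P(U < +M) = 2.5%. The interval contains +M in the remaining 100 - 2.5 - 2.5 = 95%, and those results are inconclusive. Absence can be concluded only if the half-width is smaller than M. At n = 461 the half-width is 1.96 × 15/√461 = 1.37 to 1.96 × 30/√461 = 2.74 units over the assumed SDs.

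**The case against.** The best reply is that this is a language slip. The sentence begins with the MCID, so the natural reading is that the lower limit is set against it. Other sentences in the protocol are garbled in a similar way. That is probably right about intent, and it rules out saying that the MCID was abandoned. It does not make the sentence correct as written, and no other text in either document states the intended comparison.

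A second reply is that the lower limit is the proper bound for showing a relevant increase, and the protocol does not say that an unmet criterion means no relevant change. This stands. A reader might infer that the rule would give false reassurance on QT most of the time, or would wrongly flag heart-rate falls most of the time. Neither inference is supported. The first needs an absence conclusion that the documents do not draw. The second needs an order of subtraction and a signed MCID that they do not give; with before minus after, a fall in heart rate would be handled as an increase is above.

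A third reply is that the SAP may govern, in which case the rule might never be applied. That is possible, and the documents do not settle it. It limits the practical effect but does not remove the need to reconcile the two texts.

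**Conclusion.** The concern holds as a minor defect. As written, the section 1.8 rule cannot distinguish one data set from another, and the SAP neither repeats nor corrects it. High confidence attaches to those two statements, which rest on the text alone. That a lower limit on its own cannot show a relevant decrease follows by logic, but it applies to an inferred reading of the sentence and assumes change is after minus before.

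There is no numerical effect on any planned result to report. The confidence interval and paired t-test are produced in any case; only their reading against the MCID is affected. The primary analysis of adverse-event incidence and the sample size of 461 do not depend on this rule.

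Two further readings should be avoided. The absence of an MCID value is not counted as an error, because this file is a synopsis and calls the value predetermined. Nor should a direction of concern be read into the plan. The only heart-rate threshold in the documents is a low one, in the exclusion criteria, which may suggest that a fall matters, but section 1.8 asks about changes without naming a direction.

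**What to change.** Replace the decision sentence in protocol 1.8 with the following, and put the same rule in the SAP:

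> The 95% CI of the mean change (after minus before) is compared with the predetermined MCID for that variable. A clinically relevant increase is concluded if the lower limit exceeds +MCID, and a clinically relevant decrease if the upper limit is below -MCID. Absence of a relevant change is concluded only if the whole CI lies between -MCID and +MCID. Otherwise the result is inconclusive.

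The sponsor enters its own predetermined values before analysis and states whether the rule applies to QT (named in the protocol), to QTc (also analysed in the SAP), or to both. The SAP's summaries and paired t-tests for heart rate, QT and QTc stay as they are.

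The cost is one sentence in the protocol and one added rule in the SAP, with no new data. If the rule is extended to QTc, a predetermined MCID for QTc is also needed, and the documents do not mention one. The downside is that some results become inconclusive, chiefly when the true mean change is close to the MCID.

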further assess correlations between various risk factors and incidence of AEs using variables chosen from those used in the univariate analysis (SLSTAY=0.3, a significance value of 0.3 is required for a variable to stay in the multivariate model).

MMSE and ADCS-ADL are assessed at each visit. Their changes at each visit from baseline are calculated. Factors affecting MMSE and ADCS-ADL changes are assessed with a mixed model-repeated measures using an autoregressive covariance structure. Variables are the same as those used in the univariate analysis of correlations between AEs and various risk factors

All analyses are performed with SAS 9.4 (SAS Institute Inc.; Cary, NC, USA), data is analyzed with a two-tailed hypothesis, and a *p* value < 0.05 is considered to indicate statistical significance.

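### The protocol's MCID rule judges the uncorrected QT interval; the SAP analyses QTc but names no formula and does not attach the rule to it

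*Protocol*

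**What the plan says.** Protocol 1.8 (Other Safety Data Analysis) starts with descriptive statistics: "For the QT interval and heart rate before and after treatment, the mean, median, standard deviation, maximum, minimum, 25%, 75% quantiles were used". It adds a paired t-test and a 95% confidence interval for the change, and then the decision rule: "Based on the predetermined MCID value, the 95% confidence interval is compared with the lower limit of the 95% confidence interval", in order "to determine whether the changes in QT interval and heart rate have clinical significance". QTc is not mentioned in the section.

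The same section has a second, categorical look at the ECG, a before-and-after cross-tabulation, introduced with these words, which break off before the end of the sentence: "For laboratory examination and ECG, the clinical significance judgment and frequency (or frequency) of all indexes before and after treatment are made in a cross".

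Protocol 1.6 leaves the full detail of the safety analyses to the SAP. The SAP's safety paragraph says that "changes in EKG and ECG such as HR, QT, QTc are summarized and described using means" and other descriptive statistics, followed by a paired t-test. It gives no formula for QTc and no MCID comparison for HR, QT or QTc.

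**The concern.** The QT interval lengthens when the heart slows and shortens when it speeds up, with no change in repolarisation. QT and heart rate are therefore not independent safety signals. A rule that judges QT without correction can return a conclusion about QT that only reflects rate.

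The plan treats heart rate as something that may change: Protocol 1.8 analyses it beside QT, and exclusion criterion 2 removes patients with sick sinus syndrome, higher-degree AV block or a rate below 50 bpm. The study has a single arm, so a shift in mean heart rate from any cause goes straight into the before-after difference in QT.

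At stake is a stated safety conclusion in a trial whose main purpose is safety. A rate-driven lengthening could be reported as a QT effect, and a real effect could be missed if the rate rose.

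**Working it through.** **Which document says what**

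| | Heart rate | QT | QTc |
|---|---|---|---|
| Protocol 1.8: summary, paired t-test, 95% CI | yes | yes | not named |
| Protocol 1.8: MCID rule | yes | yes | not named |
| SAP: summary, paired t-test | yes | yes | yes, no formula |
| SAP: MCID rule | none | none | none |

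QTc is analysed, but neither document ties it to the MCID. Precedence does not settle the matter. The protocol defers to the SAP, yet the SAP is dated 18 September 2016 and the protocol synopsis 9 October 2016, so the later document carries the rule written for QT.

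**How far heart rate alone moves QT**

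The documents give no QT, QTc, heart-rate or MCID value, so there is no figure of the plan's own to reproduce. What follows rests on assumptions: a baseline of 70 bpm and a Fridericia QTc (QTcF) constant at 400 ms, meaning no change in repolarisation.

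- RR = 60/HR, in seconds.
- QT = 400 × RR^(1/3).
- Bazett QTc of the same tracing = QT / RR^(1/2).

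| HR (bpm) | RR (s) | QT (ms) | Change in QT | Bazett QTc (ms) | Change in Bazett QTc |
|---|---|---|---|---|---|
| 70 | 0.857 | 380.0 | – | 410.4 | – |
| 68 | 0.882 | 383.7 | +3.7 | 408.4 | −2.0 |
| 65 | 0.923 | 389.5 | +9.5 | 405.4 | −5.0 |
| 62 | 0.968 | 395.7 | +15.7 | 402.2 | −8.2 |
| 75 | 0.800 | 371.3 | −8.6 | 415.2 | +4.7 |

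**Masking.** If the rate rises from 70 to 75 bpm, QT stays at 379.97 ms when QTcF has risen to 379.97 / 0.8^(1/3) = 379.97 / 0.92832 = 409.3 ms. A lengthening of about 9.3 ms in QTcF would leave no trace in uncorrected QT.

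**Sensitivity to the assumptions.** With the constant QTc anywhere from 400 to 440 ms:

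| HR change | QT change, Fridericia QTc constant (ms) | QT change, Bazett QTc constant (ms) |
|---|---|---|
| 70 to 68 | +3.7 to +4.1 | +5.4 to +5.9 |
| 70 to 65 | +9.5 to +10.5 | +14.0 to +15.4 |
| 70 to 75 | −8.6 to −9.5 | −12.6 to −13.8 |

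**The formula.** For the same tracings, Fridericia shows no change while Bazett shows a fall of 2.0 to 8.2 ms as the rate slows. A result labelled only QTc therefore depends on an unstated choice.

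**The case against.** The strongest reply is that the plan already lets a reader separate rate from repolarisation. Heart rate has its own summary, test, interval and place in the MCID rule. The SAP, to which the protocol defers, also tests QTc. With the three changes side by side, a purely rate-driven QT change would be visible. The ECG cross table gives a further judgement of clinical significance that does not use the MCID. And the MCID rule cannot be run as written: its value is not stated, and the interval is compared with its own lower limit.

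Much of this stands, and it rules out two stronger readings.

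- A reader might infer that every change in heart rate will be read as a change in QT, or that QT is the only clinical-significance judgement on the ECG. The separate heart-rate analysis, the QTc test and the cross table do not support that.
- A reader might infer that even a 2 bpm fall would give a false call. With 461 pairs (the protocol's sample size before the drop-out allowance) and an assumed SD of change of 20 to 30 ms, the half-width is 1.96 × SD/√461 = 1.8 to 2.7 ms. The lower limit for a 3.7 ms change is then about 1.0 to 1.9 ms. That excludes zero, but it says nothing about an MCID whose value is unknown.

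Nor do the documents predict a heart-rate change. The exclusion criteria are entry limits and give neither direction nor size.

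What does not stand is the idea that the QTc summary cures the rule. Informal comparison of three summaries is not the prespecified conclusion, and the cross table has no stated criteria. Stating the MCID and repairing the garbled comparison would still leave uncorrected QT as the parameter judged.

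**Conclusion.** The concern holds in limited form. The only MCID-based rule in either document applies to uncorrected QT and, separately, to heart rate. The SAP's QTc has neither a formula nor a link to that rule. A mean change in heart rate can therefore be judged as a QT effect, or can mask one, in the plan's stated conclusion.

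The possible size is a few milliseconds for a 2 bpm shift and roughly 10 to 15 ms for a 5 bpm fall, depending on the assumed QTc and on which correction describes the patients. These are illustrations under assumed values, not forecasts. Whether any such shift would cross the MCID cannot be determined. The point concerns a supporting safety analysis and leaves the primary endpoint, adverse-event incidence, untouched.

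**What to change.** In Protocol 1.8 and in the SAP's safety paragraph:

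- Apply the MCID judgement to the change in QTc.
- Name one correction formula in advance for all sites. Fridericia (QT/RR^(1/3)) is one option; the documents do not dictate the choice. Compute QTc for each tracing from its own QT and heart rate before averaging.
- Keep heart rate as its own parameter.
- Report uncorrected QT descriptively, without an MCID judgement.
- Use the same list of ECG parameters and the same rule in both documents.

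The cost is about a sentence in each document and no new data, since QT and heart rate are already recorded. The downside is that one formula must be chosen and defended, and the MCID must be stated on the QTc scale.
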